**Day 1: 1-2 weeks after baseline screening**

- Off Medication UPDRS
- Randomization to CR vs Sham vibrotactile stimulation
- Vibrotactile threshold measurements
- EEG recordings to assess PD-related brain oscillation
- Smell Test
- Comprehensive speech evaluation

**Day 2**

- Off medication UPDRS
- In-clinic, wearable accelerometer/gyroscope (Kinesia One; ambulatory parkinsons disease monitoring (APDM)) to capture tremor and gait
- •Patient does stimulation for 2 x2 hours with a break in between
- •Repeat UPDRS part III to asses acute CR treatment
- •Repeat In-clinic, wearable accelerometer/gyroscope (Kinesia One; APDM) to capture tremor and gait

Weekly Phone Call to assess AE's, review diary and change in medications

**Month 1- month 6 (daily, at home):**

- 2hr vibrotactile stimulation (CR vs sham), Session 1 morning
- 2hr vibrotactile stimulation (CR vs sham), Session 2 late afternoon
- Hauser diary to capture OFF time, ON time, ON time with troublesome dyskinesia, sleep time

Patients will return **at 3, 6 and 7 months** and will follow the same procedures as enrollment day 1 and 2

[figure not shown]
After the 6 month follow up, the patient will receive no stimulation for 1 month to asses long term effects and return at 7 months for a follow up assessment.

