#### Primary Hypothesis

Vibrotactile CR stimulation is not expected to cause discomfort or pain in patients as confirmed in a prior study with Parkinson's disease (IRB# 45096; Syrkin-Nikolau et al., 2018). It is expected to lead to a decrease in severity of motor symptoms from baseline to 6 months, as measured by the Movement Disorders Society's Unified Parkinson's Disease Rating scale (MDS-UPDRS) part III and patient motor diaries to capture mean time when patients' medications have worn off and are not controlling symptoms (OFF time), time when patients' medications are working effectively to control symptoms (ON time), ON time with troublesome dyskinesia, and sleep time – all factors which can be affected by Parkinson's disease. As secondary endpoints, we expect this may result in the patient's ability to reduce reliance upon dopaminergic medications, therefore we will measure changes in levodopa dose equivalency. Additionally, we will assess for improvement in non-motor symptoms of Parkinson's disease, ability to perform activities of daily living and reduction in dyskinesia, which will be measured by the Movement Disorders Society's Unified Parkinson's Disease Rating scale (MDS-UPDRS), parts 1, 2 and 4 and the Schwab and England Activities of Daily Living score. We expect patient quality of life will increase after stimulation, which will be measured by the Parkinson's Disease Questionnaire-39 (PDQ-39) scale. To get a general sense of symptom change, we will assess the patient and clinician Global Rating of Change (GRC) scale and the Patient Global Impression of Change. We will also asses speech using comprehensive speech evaluations. We predict that this decrease in symptoms will be apparent within 1 month of vibrotactile stimulation and that this treatment will be durable as assessed up to 1-months post-stimulation.

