## Statistical Analysis

Our primary hypothesis is that vibrotactile CR stimulation (i) will improve the outcome measured as On-time at least by 30% compared to the baseline after three months of usage. We also expect that (ii) the relative increase in On-time in the intervention arm (using vibrotactile CR stimulation) will be at least 20% compared to the control arm (Sham) after three months of usage. In order to test these hypotheses, we will perform Welch's t-test (paired t-test for the first hypothesis and unpaired two-sample t-test for the second hypothesis). Our power analysis shows that the sample size of 10 patients for each arm will provide 85% - 98% of power for detecting statistically significant difference based on the mean On Time of 7.3 at baseline and SD of 2-2.5 that were obtained from our preliminary study.

**Based on this power analysis, we are planning to enroll a minimum of 60 patients. 30 patients will be randomized to receive the real stimulation initially. The remaining 30 will be randomized to receive sham stimulation, using dedicated sham stimulation pattern.**

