## Protocol summary

### **Day 0: Baseline testing (screening):**

- Patient medical history
- General physical exam
- Neurological exam
- Concomitant and PD medications (Levodopa equivalents in mg)
- OFF MDS-UPDRS, part III 12 hour washout of short-acting and 24 hour washout of long acting levodopa containing medications)
- ON MDS-UPDRS, part III (1-2 hours after taking levodopa)
- MOCA and SCOPA
- Clinically trained staff (MD, PA, or RN) will review the consent form in detail with the participant and answer any questions about the study. After consent, the participant will be enrolled in the study and randomized to CR or sham.

- Blinding form – patient
- Blinding form – assessing clinician (MD, PA, RN)

*Surveys to be completed after accepted into study and prior to the 1st day of enrollment. Survey will be completed on medication and sent via email*

1. MDS-UPDRS, Parts I-II, and IV
2. Parkinson's Disease Questionnaire-39 (PDQ-39) scale
3. Schwab and England Activities of daily living score
5. Beck depression and Anxiety inventory

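### The readable schedule lists no On-time measure before the first listed stimulation on Day 2, yet hypothesis (i) is a paired test of 3-month On-time against baseline

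*Combined protocol and SAP*

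**What the plan says.** The Statistical Analysis section sets two On-time hypotheses at three months. The first is that stimulation "will improve the outcome measured as On-time at least by 30% compared to the baseline after three months of usage". The second concerns "the relative increase in On-time in the intervention arm" relative to sham, put at 20% or more. The tests are a "paired t-test for the first hypothesis and unpaired two-sample t-test for the second hypothesis". The Primary Hypothesis section also relies on change from baseline: "It is expected to lead to a decrease in severity of motor symptoms from baseline to 6 months", with motor diaries among the measures.

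The Protocol summary lists procedures by day:

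- **Day 0:** history, examinations, OFF and ON MDS-UPDRS III, cognitive scales, consent and blinding forms. A survey list follows ("Surveys to be completed after accepted into study and prior to the 1st day of enrollment"): MDS-UPDRS I, II and IV, PDQ-39, Schwab and England, and the Beck inventories. No diary is listed, and the numbering runs from 3 to 5.
- **Day 1** ("1-2 weeks after baseline screening"): OFF UPDRS, vibration thresholds, EEG, smell and speech. No diary is listed.
- **Day 2:** OFF UPDRS and an in-clinic wearable for tremor and gait, then the first listed stimulation. A line after the Day 2 items has staff look over the diary in a weekly telephone call.
- **Month 1 to month 6, at home:** two daily stimulation sessions and "Hauser diary to capture OFF time, ON time, ON time with troublesome dyskinesia, sleep time".
- **Months 3, 6 and 7:** the Day 1 and Day 2 procedures again.

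The Data collection section describes the source of On-time differently, as an electronic motor diary with a wearable sensor, and gives no time points.

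**The concern.** A paired t-test needs two On-time values per patient, one of them from before treatment. The analysis text presupposes that value, but the schedule a site would follow does not ask for it. The only scheduled diary item sits beside twice-daily stimulation.

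If the schedule is complete as printed, hypothesis (i) cannot be run as specified. The relative increase in hypothesis (ii) also has no patient-level starting point, so the arms could be compared only on their 3-month values. A pre-stimulation diary cannot be collected after a patient has started, so the gap has to be closed before enrolment rather than at analysis.

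A smaller gap of the same kind affects PDQ-39 and Schwab and England. The Primary Hypothesis section expects both to improve, but the Protocol summary lists them only before Day 1, and the follow-up visits repeat only the Day 1 and Day 2 procedures.

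**Working it through.** **1. Is there any pre-stimulation On-time value?** Each place where one could come from:

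| Place | On-time content | Before first listed stimulation? |
|---|---|---|
| Day 0 list and surveys | none in readable text | – |
| Day 1 list | none | – |
| Day 2 list | in-clinic wearable, tremor and gait only | does not give On-time |
| Weekly call | reviews a diary; no start date | printed after the Day 2 stimulation items |
| Month 1 to month 6 | Hauser diary | no |
| Study Procedures, Day 7 and Day 28 visits | unspecified assessments | no |
| Primary Hypothesis; Data collection | diary named | no time point given |
| Statistical Analysis, mean 7.3 | from the preliminary study | not these patients |

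No row supplies the value. The 7.3 cannot stand in for it, because a paired test uses each patient's own baseline.

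**2. The plan's own power figure.** Inputs from Statistical Analysis: mean 7.3, SD 2 to 2.5, 10 per arm, stated power 85% to 98%. Alpha, sidedness and within-patient correlation are not given. I assume two-sided 0.05, take the SD as the between-patient SD, and read On-time in hours. Power is from the noncentral t.

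- Hypothesis (i): 0.30 × 7.3 = 2.19 h. With SD of change equal to SD (correlation 0.5), noncentrality = 2.19/(SD/√10) = 3.46 (SD 2) or 2.77 (SD 2.5), giving power 0.868 or 0.694.
- Hypothesis (ii): 0.20 × 7.3 = 1.46 h, giving 0.339 or 0.235 with 10 per arm.

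The stated range is not reproduced from the stated inputs. It is approached for the paired test only by adding an unstated correlation of about 0.66 to 0.68 (85–87% at SD 2.5, 96–97% at SD 2). That is a separate matter, and the present point does not depend on it.

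**3. What remains without a baseline.** Hypothesis (ii) on 3-month values, 30 per arm. Noncentrality = difference/(SD × √(2/30)), with √(2/30) = 0.2582 and 58 df. The 20% can be read as 20% of 7.3 (1.46 h), or as 20% of the 3-month level of 7.3 × 1.30 = 9.49 (1.898 h).

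| Difference | SD | Noncentrality | Power |
|---|---|---|---|
| 1.46 h | 2 | 1.46/0.5164 = 2.83 | 0.794 |
| 1.46 h | 2.5 | 1.46/0.6455 = 2.26 | 0.604 |
| 1.898 h | 2 | 1.898/0.5164 = 3.68 | 0.951 |
| 1.898 h | 2.5 | 1.898/0.6455 = 2.94 | 0.824 |

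**4. What a baseline would add to hypothesis (ii).** For an unpaired t-test on change, the SD becomes SD × √(2(1 − r)). For 1.46 h and assumed r = 0.3/0.5/0.7, power is 65/79/95% (SD 2) or 47/60/82% (SD 2.5). Compared with 79% and 60% on 3-month values, a baseline helps this test only if r exceeds 0.5.

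**The case against.** **Text may have been lost.** The survey numbering skips 4, where a self-report item could have stood, and figures are not shown in Study Procedures and after the follow-up line of the Protocol summary. The hypotheses plainly intend a baseline. This stands as a limit: the finding is that the readable text lists no pre-stimulation On-time measure. A reader might infer that none will be collected, and the documents do not show that. Even so, no readable text defines baseline On-time or its number of days.

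**A diary is mentioned before the Month 1 heading.** This is true of the weekly call, so it would be wrong to say that the day lists never mention one. The line has no start date, follows the Day 2 stimulation items and schedules no baseline.

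**First stimulation is not settled.** Inclusion criterion 4 speaks of sessions on two consecutive days at the start, while the lists show stimulation only on Day 2. The passages should be reconciled. An earlier start would not supply a baseline.

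**The randomised test does not need a baseline.** This stands. Hypothesis (i) is a within-arm comparison that does not involve sham; hypothesis (ii) remains possible on 3-month values.

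**The questionnaires are in the data list.** The Data collection section names PDQ-39 and Schwab and England without limiting the visits, and the Day 7 and Day 28 assessments are unspecified. So their follow-up is unlisted, not ruled out.

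**Conclusion.** The point holds in a limited form. The analysis needs a pre-stimulation On-time value that the readable schedule does not list. Unless a line was lost, a site following that schedule could not run hypothesis (i), and hypothesis (ii) could be run only on 3-month values. Its power would then be 79% or 60% for 1.46 h (SD 2 or 2.5), or 95% or 82% for about 1.90 h. These figures assume two-sided 0.05, 30 analysed per arm, equal SDs and no dropout.

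Two stronger readings are not supported. One is that the comparison with sham is lost; step 4 of the working shows that a baseline would not even raise the power of the planned t-test unless r exceeds 0.5. The other is that the first month's diary will serve as baseline and dilute the effect. No section proposes this, and its size would rest on invented fractions. The prediction "We predict that this decrease in symptoms will be apparent within 1 month of vibrotactile stimulation" is only a reason to rule that use out in writing. OFF MDS-UPDRS III is listed on Day 0, Day 1 and Day 2 before stimulation and is not affected.

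This should be fixed: it concerns a stated primary hypothesis, and a missing value cannot be recovered later.

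**What to change.** 1. Confirm whether a schedule line was lost: survey item 4 and the figures in Study Procedures and the Protocol summary.
2. If none was lost, list the Hauser diary for a stated number of days in the existing 1-2 week interval between Day 0 and Day 1, before any stimulation. Define baseline On-time as the mean of those days.
3. State that no on-treatment diary serves as baseline.
4. Name one On-time source, so that the Protocol summary (Hauser diary) and Data collection (wearable electronic diary) agree.
5. List PDQ-39 and Schwab and England at the follow-up visits.

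The cost is a schedule amendment, a few diary days and repeated questionnaires for each patient. No new visits are needed.

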## Vibro-tactile Stimulation Protocol and Device Description

[figure not shown]
Typical tactile stimulation parameters are cyclic with cycle period between 200ms and 1000ms. During each stimulation cycle, each tactor delivers vibratory stimulation once, with vibration pulse length of up to 250 ms per pulse (1 for each finger). Typical cumulative stimulation duration is between 1 and 4, typically 2 hours per day.

Vibro-tactile coordinated reset (CR) neuromodulation therapy system is a commercially available, non-invasive, battery-operated mobile device. The device consists of a handheld component with vibro-tactile stimulators (tactors) and is fitted and programmed by a qualified healthcare professional familiar with treatment of Parkinson's disease (e.g., neurologists and/or their clinical research assistants).

The healthcare professional sets the individual stimulation parameters via a PC application called 'neuro player' and programs the patient device directly via USB connection or via an SD card, which is thereafter plugged into the patient device. The patient device is wired to the vibro-tactile stimulators or controllers that can be hung around the neck of the patients, which allows free movement of the patient. The stimulating tactors (**Figures 2 and 3**) are implemented inside a glove and are flexibly and individually attached to the fingertips (**Figure 4**) via elastic Velcro bands (**Figure 1**).

**Figure 2: Fingertip Stimulator**

[figure not shown]
For best results, housing and contactor should remain in contact with skin.

Velcro or other attachment may be applied to this side as long as it is clear of the center hole.

**Figure 3: Individual Tactor**

**Figure 4: Fingertip definition**

A display presents information about battery status and progress of the schedule therapy application. Via a push button, the device and the therapy it delivers can be turned on or off.

#### Risks

The same tactile stimulator system has been studied in a pilot and published in 2018 (Syrkin-Nikolau et al., 2018; Stanford IRB-approved study, IRB# 45096). —at the time not yet integrated into a glove—was already IRB approved and successfully used in epilepsy patients under the supervision of [name] in the research study at Stanford University performed under protocol #31684. Preliminary testing by the researchers has not indicated

any discomfort or worsening of symptoms. Therefore, Neurotherapies Reset has determined that the vibro-tactile CR therapy does not pose a significant risk to the human subjects; the vibro-tactile CR device, therefore, has been classified as a non-significant risk (NSR) device. However, given that the device is not yet FDA approved, and has not been tested under this exact protocol before, there is a possibility the stimulation could be uncomfortable or even painful for some patients, could worsen one's symptoms or could have other unexpected effects including psychological complications. See the Withdrawal section below for no-go criteria. If there is any discomfort, the researchers can shut off tactile stimulation at any time.

#### Benefits

The patient's Parkinson's disease symptoms may be reduced, and quality of life may be increased, as a result of the vibratory stimulation, either for a transient period of time such as a few hours post-stimulation, or possibly even for several weeks to months. Ultimately, this pilot study could provide evidence that vibro-tactile stimulation is a safe and effective method to treat symptoms of Parkinson's disease, which would provide a much-needed alternative to medication, surgery and other invasive procedures in the future.

#### Withdrawal

Each Subject, the Sponsor or its designee and the Investigator reserve the right at any time to terminate a Subject's participation in the clinical investigation.

Possible reasons for withdrawal from the study:

1. Subject voluntarily withdraws consent
2. Subject develops an Adverse Event (AE) that would not allow him or her to continue in the study
3. Subject has an AE which in the opinion of the Investigator warrants withdrawal from the study. Such an AE would include anything unexpected that requires hospitalization. The Sponsor or its designee must be notified within 2 business days
4. A decision is made by the Subject and/or Investigator that the Subject should be withdrawn from the study

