**Stanford Neurosurgery**

**Investigator's Agreement**

By signing below I confirm that I have read this protocol and agree that it contains all necessary details for conducting this study. I will conduct the study according to the procedures described in this protocol.

---

Principal Investigator's Signature

---

Date

---

Principal Investigator's Name

---

Principal Investigator's Signature

---

Date

---

Principal Investigator's Name

Site Address:      Stanford University Medical Center  
                          [name]  
                          [name]

*Our study to evaluate peripheral vibrotactile coordinated reset stimulation for Parkinson's disease* seeks to explore the safety and efficacy of an experimental non-invasive method to aid in the symptoms of Parkinson's disease. The purpose of the study is to verify the safety and tolerability of non-painful sensory (tactile) vibratory stimulation delivered to the fingertips of patients with Parkinson's disease.

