## Data collection, transfer and storage

**Clinical data:** We will complete a log that documents all patients who are treated with vibro-tactile stimulation. For patients who are considered but not enrolled in this trial, the reason for exclusion will be recorded. The data collection process will entail site staff completing case report forms (CRFs) for the initial capture of research data during participant encounters and the data will be entered into a secure database. Clinical data obtained on the case report forms will include patient demographics, previous medical conditions, Concomitant and PD medications (Levodopa equivalents in mg), MDS-UPDRS, Parts I-II, Off MDS-UPDRS, part III 12 hour washout of short-acting and 24 hour washout of long acting levodopa containing medications), On MDS-UPDRS, part III (1-2 hour after levodopa medication), MDS-UPDRS, part IV, Collect data from electronic motor diary – wearable (accelerometer/gyroscope) to capture off time, on time, on time with troublesome dyskinesia, sleep time, PDQ-39, Schwab and England Activities of daily living score, Patient and clinician Global Impression of change scale and speech assessments.

All data will be accessed only by Stanford researchers on-site.

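### The Withdrawal section makes adverse events possible grounds for leaving the study without separating that from stopping stimulation, and no section provides for follow-up after such a withdrawal

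*Combined protocol and SAP*

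**What the plan says.** The Withdrawal section gives the subject, sponsor and investigator the right to end a subject's participation, and then lists four possible reasons for leaving the study. Two are AEs.

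- Item 2: "Subject develops an Adverse Event (AE) that would not allow him or her to continue in the study".
- Item 3: an AE that the investigator judges to warrant withdrawal. The section adds: "Such an AE would include anything unexpected that requires hospitalization". The text sets no condition on relatedness to the device. The only action attached is notice to the sponsor within two business days.

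Item 4 covers any decision by the subject or the investigator that the subject should be withdrawn.

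The Risks section points here for its stopping rules ("See the Withdrawal section below for no-go criteria"). It also allows a separate step for discomfort: "If there is any discomfort, the researchers can shut off tactile stimulation at any time".

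AEs are sought during participation. The Protocol summary, under Day 2, plans this: "Weekly Phone Call to assess AE's, review diary and change in medications". Patients keep a daily home diary from month 1 to month 6 and return at months 3, 6 and 7.

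**The concern.** The Investigator's Agreement section states the aim: "The purpose of the study is to verify the safety and tolerability of non-painful sensory (tactile) vibratory stimulation". For that aim, a patient who leaves because of an AE is among the most informative in the trial. The Withdrawal section ends that patient's participation, and nothing in the plan then provides for learning how the event resolved or whether others followed.

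Efficacy data are exposed too. The Statistical Analysis section compares On-time between arms at three months, so a patient who exits earlier may have no value for that comparison. The Primary Hypothesis section also names change in MDS-UPDRS part III from baseline to 6 months, and exit before month 6 can lose that outcome. The Statistical Analysis section gives no rule for withdrawals or missing values.

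Ending follow-up is not generally needed to protect the patient, because turning off the device ends exposure to vibration. Under the Sham control section, sham patients receive zero amplitude, so for them leaving the study removes no vibration at all.

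**Working it through.** The plan gives no figure on this point to reproduce. The check is a reading of the sections together, followed by a count of the scheduled follow-up at stake.

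**Reading the sections together**

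1. Withdrawal: the listed events lead to leaving the study. The section has no step in which stimulation stops and the patient remains in follow-up.
2. Risks: stimulation can be shut off for discomfort. The calls and visits in the Protocol summary are not conditional on stimulation, so these patients appear to stay on schedule. They are a separate group from those withdrawn.
3. Protocol summary: weekly AE calls, diary and visits are planned for participants. None is extended to a withdrawn patient. The off-stimulation visit at month 7 is the planned assessment after the month-6 visit and is not follow-up for AE withdrawals.
4. Statistical Analysis: paired and two-sample t-tests, with no provision for withdrawn patients.

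So once a patient is withdrawn under items 2 to 4, no visible section continues AE or outcome collection.

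**Scheduled follow-up that can be lost**

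Inputs: visits at months 3, 6 and 7; daily diary to month 6; weekly calls with no stated end date, so both month 6 and month 7 are shown. Assumptions: 30.44 days per month, and exit at month *m*. The four exit times are chosen for illustration.

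- Diary days lost = (6 − m) × 30.44
- Diary days lost before month 3 = (3 − m) × 30.44
- Calls lost = (6 − m) × 30.44 / 7, or (7 − m) × 30.44 / 7 if calls run to month 7

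| Exit | Visits lost | Diary days lost | Of these, before month 3 | Calls lost, to month 6 | Calls lost, to month 7 |
|---|---|---|---|---|---|
| Month 1 | 3 | 5 × 30.44 = 152 | 2 × 30.44 = 61 | 152.2 / 7 = 22 | 182.6 / 7 = 26 |
| Month 2 | 3 | 4 × 30.44 = 122 | 1 × 30.44 = 30 | 121.8 / 7 = 17 | 152.2 / 7 = 22 |
| Month 4 | 2 | 2 × 30.44 = 61 | 0 | 60.9 / 7 = 9 | 91.3 / 7 = 13 |
| Just after the month-6 visit | 1 | 0 | 0 | 0 | 30.44 / 7 = 4 |

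The month-3 On-time outcome is at risk only in the first two rows. The table shows what one withdrawn patient can miss. It says nothing about how many patients will be withdrawn, which the documents do not state.

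**The case against.** The strongest reply is that the section is softer than it may look. Its reasons are only possible ones. Item 2 applies only when the AE prevents continuing in the study, and item 3 rests on the investigator's opinion. This stands: a reader might infer that an unexpected hospitalization automatically removes a patient, and the text does not say that. What remains is that the section names such an event as one that warrants leaving, and offers the investigator no option of stopping stimulation while continuing follow-up.

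Second, a stop-stimulation route exists in the Risks section. That also stands, and it confines the point to patients actually withdrawn. It would be wrong to count those whose device is shut off for discomfort as lost.

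Third, a reader might infer from the case report form list in the data collection section that AEs go unrecorded, since it names no AE item. The documents do not support that. The list is not presented as complete, and it also leaves out planned assessments such as MOCA, SCOPA, the Beck inventories and EEG. Weekly AE assessment is scheduled, and a log of treated patients is planned.

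Fourth, consent pages are not in the reviewed copy and could hold terms on data collected after withdrawal. So the gap is one in the visible text.

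Fifth, the statistical hypotheses concern results after three months of device use, so adding off-stimulation data to the comparison with sham would change the question. That is correct. Collecting the data and choosing how to analyse them are separate decisions.

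**Conclusion.** The point holds in a limited form and merits an amendment. AEs, expressly including unexpected hospitalization, are possible and discretionary grounds for leaving the study. Stopping stimulation is not separated from ending follow-up, and no visible section provides for AE or outcome collection afterwards. Each patient withdrawn this way can leave with the AE outcome unknown and, depending on timing, miss one to three of the later visits. The month-3 On-time outcome is at risk only if exit comes before month 3.

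A reader might go further and infer that the comparison of active stimulation with sham will be biased in a particular direction. The documents do not support that: the rule covers both arms, no withdrawal rate is given, and nothing shows how leavers would differ from stayers. The size and direction of any bias cannot be determined, so the case rests mainly on the safety purpose.

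The conclusion assumes that a patient withdrawn from the study has no further scheduled contact, which is the natural reading, and that the removed consent pages do not say otherwise.

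**What to change.** Amend the Withdrawal section as follows.

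1. Make AEs, including unexpected hospitalization, and investigator decisions under item 4 reasons to stop stimulation. State this separately from withdrawal of consent for follow-up.
2. Keep the investigator's right to end participation where continued follow-up would be unsafe, and leave the two-business-day notice as it is.
3. Unless consent is withdrawn, follow the AE to its outcome through the weekly calls. Keep the patient on the diary and the month 3, 6 and 7 visits as far as medically feasible.
4. Record the AE outcome, and the date of and reason for stopping.

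One sentence in the Risks section should confirm that a patient whose stimulation is shut off for discomfort stays on the schedule.

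Decide separately, and in advance, whether off-stimulation data enter the main test of the comparison with sham or a supporting analysis by randomised arm. The wording about device use in the Statistical Analysis section leaves that choice open.

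The cost is a protocol amendment, three recorded items, and visit burden and staff time for a few patients whose calls and two-day visits would otherwise end. No new procedure is needed, since every patient is already to be assessed off stimulation at month 7.
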